2.3.3 Exploratory endpoint

Incidence of anti-N8-GP binding antibodies

Number of positive/negative samples will be summarised by visit and listed.

Incidence of anti-PEG binding antibodies

Number of positive/negative samples will be summarised by visit and listed. Furthermore, plots will be created of incremental recovery in relation to PEG antibody status at baseline and during the trial. Rules for exclusion of FVIII activity measurements are defined in the paragraph: "Pre-dose FVIII activity levels for patients on N8-GP prophylaxis".

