#### **Anti-N8-GP antibodies**

A radioimmunoassay using radiolabelled N8-GP will be used for measuring antibodies against N8-GP and validated according to guidelines. If the sample was found positive for anti-N8-GP binding antibodies a cross-reactivity test will be performed to identify if the antibodies could cross-react with endogenous FVIII. The level of antibodies will be determined by diluting samples to obtain a titre.

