**Novo Nordisk**

samples are tested in a confirmatory assay to distinguish between true anti-PEG antibody positive and false positive samples. If the test is confirmed positive, a titre determination will be applied to establish the level of anti-PEG antibodies.

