#### **Incidence of anti-PEG binding antibodies**

Number of positive/negative samples will be summarised by visit and listed. Furthermore, plots will be created of incremental recovery according to PEG antibody status at baseline and during the trial. Rules for exclusion of FVIII activity measurements are as defined in the paragraph on: "Pre-dose FVIII activity levels on N8-GP prophylaxis".

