Furthermore, success rates will be estimated with 95% confidence intervals using logistic regression accounting for repeated measures within patient assuming compound symmetry working correlation. Age group will be included as a factor and modelling done separately for each treatment regimen. This estimation will be done both including missing haemostatic evaluations as failures and excluding missing evaluations.

Summaries will also be done for the following further sub-groupings:

- Cause of bleed (spontaneous and traumatic). Estimation of success rates and 95% confidence intervals using above described modelling will also be performed (both including missing as failures and excluding missing).
- Location of bleed.
- Severity.
- Country.
- Race
- Ethnicity

Number of N8-GP injections required per bleeding episode

This endpoint will be summarised and listed.

Pre-dose FVIII activity levels for patients on N8-GP prophylaxis

The following rules will be implemented for FVIII pre-dose and post-dose activity to ensure data representing steady-state on a given treatment regimen:

- FVIII activity data prior to the 4th prophylaxis dose will be excluded for each switch in treatment regimen
- FVIII activity data will be excluded if post-dose activity is \leq pre-dose FVIII activity
- FVIII activity data will be excluded if post-dose sample is taken more than 90 minutes after dosing
- FVIII activity results will be excluded for plasma samples defrosted during transit.

Statistical Analysis Plan
Trial ID: NN7088-4410
UTN: U1111-1202-2780
EudraCT No.: 2017-003788-36

~~CONFIDENTIAL~~

Date:	10 September 2020	Novo Nordisk
Version:	2.0	
Status:	Final	
Page:	9 of 11	

The pre-dose FVIII activity levels will be modelled to get an estimate of the pre-dose level for N8-GP at steady-state. The model will be a mixed model on the logarithmic plasma activity levels with age as a factor and patient as a random effect. Separate modelling will be performed for each treatment regimen. Plasma concentrations below lower limit of quantification (LLOQ) will be set to half the value of the LLOQ. The estimated pre-dose FVIII level will be presented together with the 95% confidence intervals.

A sensitivity analysis will be performed including all activity results except activities measured in relation to the first 4 prophylaxis doses after switch of treatment regimen.

Pre-dose activity will furthermore be summarised by visit and treatment regimen.

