2.5 Additional efficacy related tables/figures/listings

Post-dose activity measurements will be modelled and presented in the same forms as pre-dose activity measurements, see section on “Pre-dose FVIII activity levels on N8-GP prophylaxis”.

Incremental recovery is defined as post-dose FVIII activity minus pre-dose FVIII activity and divided by the administered dose. Incremental recovery will be summarised by visit and listed.

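### Anti-PEG and anti-N8-GP titres are measured, but no planned summary or plot commits to using them; plot recovery against anti-PEG titre beside the status plot and summarise both titres.

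*SAP*

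**What the plan says.** **Measurement (Protocol 9.8.8.2, Antibody assays).** Anti-PEG samples go through a screening assay and then a confirmatory assay. "If the test is confirmed positive, a titre determination will be applied to establish the level of anti-PEG antibodies". For anti-N8-GP antibodies, "The level of antibodies will be determined by diluting samples to obtain a titre".

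**Analysis (SAP 2.3.3; same plan in Protocol 10.3.3).** The same sentence serves for each antibody: "Number of positive/negative samples will be summarised by visit and listed". For anti-PEG only, the SAP adds that "plots will be created of incremental recovery in relation to PEG antibody status at baseline and during the trial"; the protocol has "plots will be created of incremental recovery according to PEG antibody status at baseline and during the trial". Neither document defines status, and neither mentions titre in the analysis text. No test or model is attached to the plots.

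**Recovery and exclusions.** SAP 2.5 gives the quantity plotted: "Incremental recovery is defined as post-dose FVIII activity minus pre-dose FVIII activity and divided by the administered dose". SAP 2.3.3 says that the plots follow the FVIII activity exclusion rules of SAP 2.3.2.1. One of those rules is that "FVIII activity data will be excluded if post-dose activity is" equal to or below the pre-dose value.

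**The concern.** A titre is an ordered measure of how much antibody is present. Status stands directly after counts of positive and negative samples, so its natural reading is the same two-way split. Two things then follow.

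- A patient just above the assay threshold and a patient with a high titre fall in the same group. If recovery falls as titre rises, the low-titre positives pull the positive group towards the negatives.
- All patients come from earlier trials of the same product, so some may be positive at entry. For them the informative change over two years is a rise in titre, and that moves no count and no grouping.

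The recovery plots are the only output the SAP commits to that relates anti-PEG antibodies to how the drug behaves. They could look reassuring while the few patients with high titres have lost recovery.

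**Working it through.** **1. The plan's own figures.** The only design figure is the 0.02 upper bound for an adverse event not seen in 150 patients (SAP 2.1). It reproduces: 1 − 0.05^(1/150) = 0.0198, or 3/150 = 0.0200. It has no bearing on the antibody plots. The documents give no anti-PEG frequency, titre distribution or spread of recovery, so steps 3 and 4 rest on assumed inputs.

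**2. Where titre appears.**

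| Item | Anti-PEG | Anti-N8-GP |
|---|---|---|
| Titre determined (Protocol 9.8.8.2) | Yes, confirmed positives | Yes |
| Summary by visit (SAP 2.3.3) | Positive/negative counts | Positive/negative counts |
| Listing (SAP 2.3.3) | Yes, content not stated | Yes, content not stated |
| Recovery plot (SAP 2.3.3) | By status, undefined | None |
| Exploratory PK/PD (SAP 2.4) | Optional, unspecified | Optional, unspecified |

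Titre is measured for both antibodies and committed to in no summary or plot.

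**3. How pooling dilutes an effect.** Assume that positives fall on titre steps 1 to 7 with shares 35, 25, 16, 11, 7, 4 and 2%.

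- Mean step = 0.35×1 + 0.25×2 + 0.16×3 + 0.11×4 + 0.07×5 + 0.04×6 + 0.02×7 = 2.50.
- *Graded effect.* If recovery falls in proportion to step and reaches 1.5 SD at step 7, the mean of the positive group falls by 1.5 × 2.50/7 = 0.54 SD.
- *High titres only.* If recovery falls by 1.5 SD only at step 5 or above, the share affected is 7 + 4 + 2 = 13%, and the mean of the positive group falls by 1.5 × 0.13 = 0.195 SD. With 20% of 150 patients positive, that is 30 positives, of whom 30 × 0.13 = 3.9 are affected on average.
- *Uniform effect.* If every positive loses 0.5 SD, the group falls by 0.5 SD and nothing is diluted.

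**4. Which display shows the effect better.** The plan has no test. As a stand-in for how visible a pattern would be, take the share of simulated trials in which a two-sided 5% test finds an association between recovery and status, or between recovery and titre step (negatives at zero). The set-up is 150 patients, one recovery value each, the titre shares above, and 8,000 trials per cell.

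| Positive | Graded: status / titre | Step 5 or above only: status / titre | Uniform 0.5 SD: status / titre |
|---|---|---|---|
| 5% | 31% / 40% | 12% / 21% | 28% / 22% |
| 10% | 50% / 63% | 13% / 32% | 45% / 34% |
| 20% | 72% / 87% | 16% / 48% | 68% / 51% |
| 30% | 83% / 95% | 18% / 61% | 80% / 60% |

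A second set of assumptions gave the same pattern: 170 patients, 20% positive, geometric titre steps with parameter 0.45 and maximum 7, SD of log recovery 0.25. The figures for status and titre were 64% and 82% with recovery 5% lower per step, 25% and 54% if only steps above the lowest counted, and 58% and 41% for a uniform 10% loss.

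**5. The exclusion rule.** Recovery = (post − pre)/dose, and dose is positive, so post ≤ pre is the same condition as recovery ≤ 0. The rule removes exactly the samples with the most extreme loss of recovery. Adding titre to the plot would not bring them back.

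**The case against.** The case for leaving the plan alone has five parts.

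- **The endpoint is incidence.** Protocol 4.1.3 and 4.2.3 ask for the incidence of these antibodies, and positive/negative counts answer that directly. Anti-PEG positives have also passed a confirmatory assay, so the split is not a bare screening cut. This stands, and the counts should stay. It does not cover the recovery plots, which ask a different question.
- **There is no test to lose power.** A reader might infer that the plots have lost much of their ability to show an effect. The documents do not support that. The plots are descriptive, the inputs in steps 3 and 4 are assumed, and the comparison reverses if all positives are affected alike.
- **Titres may be reported anyway.** A reader might also infer that the plan discards them. That too is more than the text says: status is undefined, listing content is unspecified, and SAP 2.4 leaves room for further PK work. But a listing does not relate titre to recovery, and the PK clause commits to nothing.
- **Low recovery is visible elsewhere.** Recovery is summarised by visit and listed (SAP 2.5). Values below expectation are a named ground for suspecting inhibitors (Protocol 9.8.8.1), and the work-up in Appendix 2 includes anti-PEG antibodies. This stands and limits the harm. If the plots show individual points, low values would be seen there too, though not linked to titre.
- **A fitted slope would not help much.** With few high-titre patients, looking at individuals tells as much. A mixed model with a plain random patient effect also blends within- and between-patient differences, so it does not give a within-patient slope. This stands, and no model is proposed.

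**Conclusion.** The point holds as a gap in the analysis text. Titres are measured for both antibodies, and no planned summary or plot commits to using them. If status means positive or negative, the recovery plots can hide an effect that grows with titre, and a rise in an already positive patient changes no planned count or grouping.

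No size can be put on the loss from the documents. Under the assumptions shown, titre is the better display for a graded or high-titre effect and status for a uniform one. Since the shape of any effect is unknown, the conclusion is to show both and not to replace one with the other. The simulated percentages illustrate direction only and should not be quoted as the trial's power. The removal of every recovery of zero or less follows from the definition and needs no assumption.

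The endpoint is exploratory and no confirmatory result is touched: a cheap improvement.

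**What to change.** In SAP 2.3.3 and Protocol 10.3.3:

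1. Define status as confirmed positive or negative, and keep the status plot.
2. Add a patient-level plot of incremental recovery against anti-PEG titre at the same visit, on a log2 scale with negatives at zero.
3. Summarise anti-PEG and anti-N8-GP titres of positive samples by visit (median and range), and show each patient's highest post-baseline titre against his baseline titre.
4. Repeat the recovery plots without the rule that drops samples whose post-dose activity is at or below pre-dose. The other exclusion rules can stay.

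The cost is SAP and protocol wording, one new plot, a repeat of the plots without that rule, and a small titre summary. The titres are already produced, so no new sampling or assay is needed. The drawback is a few more descriptive exploratory outputs, possibly resting on few positive patients.

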2.3.4 Interim analyses

Interim analysis may be performed, if deemed appropriate.

2.4 Pharmacokinetic and/or pharmacodynamic modelling

Statistical Analysis Plan
Trial ID: NN7088-4410
UTN: U1111-1202-2780
EudraCT No.: 2017-003788-36

~~CONFIDENTIAL~~

Date: 10 September 2020
Version: 2.0
Status: Final
Page: 10 of 11

Novo Nordisk

Data from the trial may be used for exploratory pharmacokinetic and/or pharmacodynamic analysis as needed.

2.5 Additional efficacy related tables/figures/listings

Post-dose activity measurements will be modelled and presented in the same forms as pre-dose activity measurements, see section on “Pre-dose FVIII activity levels on N8-GP prophylaxis”.

Incremental recovery is defined as post-dose FVIII activity minus pre-dose FVIII activity and divided by the administered dose. Incremental recovery will be summarised by visit and listed.

2.6 Additional safety related tables/figures/listings

All safety parameters not addressed above such as laboratory parameters, vital signs and physical examinations will be summarised by visit.

Laboratory reference ranges and abnormal laboratory values will be listed.

Furthermore, the following safety related output will be created.

Frequency of adverse events that are reported within the system organ classes nervous system, psychiatric, hepatic and renal disorders

Will be summarised and listed.

Changes in laboratory assessments, including hepatic and renal function parameters

Individual profiles of laboratory parameters will be created by age group as plots of parameter values vs. time since first dose in trial.

Estimated glomerular filtration rate (eGFR) in ml/min per 1.73 m² will be calculated e.g. using following formula:

For ≥ 18 years of age: $\text{Constant} * s\text{-cr}^{-1.154} * \text{age}^{-0.203} * [1.212 \text{ if black or African American}] * [0.742 \text{ if female}]$, where $\text{constant} = 175 * (88.4^{1.154})$ ⁽¹⁾

For < 18 years of age: $\text{Constant} * \text{height (cm)} / s\text{-cr}$, where $\text{constant} = 0.413 * 88.4$ ⁽²⁾

eGFR will also be plotted vs. baseline value.

Polyethylene glycol (PEG) concentration in plasma

There is no evidence from our data of any clinical consequences due to long-term exposure to PEG. However, to accommodate a general concern from the authorities regarding systemic accumulation of PEG, concentration of PEG in plasma will be measured at visit 3 plus at the end-of-trial visit, and summarised for each visit.

Statistical Analysis Plan
Trial ID: NN7088-4410
UTN: U1111-1202-2780
EudraCT No.: 2017-003788-36

~~CONFIDENTIAL~~

Date: 10 September 2020
Version: 2.0
Status: Final
Page: 11 of 11

Novo Nordisk

3 Changes to the statistical analyses planned in the protocol

There are no changes to the statistical analyses described in the protocol. The text in Section 2 “Statistical Considerations” of this SAP is identical to the text in the “Statistical Considerations” section in the protocol.

4 References

1. A More Accurate Method To Estimate Glomerular Filtration Rate from Serum Creatinine: A New Prediction Equation for the Modification of Diet in Renal Disease Study Group [name]; [name]; Julia [name]; [name]; Nancy Rogers, MS; and [name], *Annals of Internal Medicine* March 1999; 130: 461

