**Figure 5-1: Overview of prophylaxis regimen options in pathfinder8**

The investigator will decide which treatment arm the patient should be allocated to taking previous treatment regimen and bleeding tendency into account. Only patients on once weekly dosing or on-demand treatment upon entry into pathfinder8 are allowed to enter the once weekly treatment arm. Twice and three times weekly dosing is allowed for all patients. The investigator should evaluate the need for an intensification to the three times weekly dosing regimen if a patient experienced/experiences recurrent spontaneous bleeding episodes. The treatment regimen can be changed to twice or three times weekly during the course of the trial if deemed clinically relevant by the investigator.

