**Novo Nordisk**

The administered dose of 75 IU/kg BW corresponds to the highest single dose tested in the clinical trial programme for N8-GP. Selected patients that during participation in the NN7088-3859 (pathfinder2) trial, due to a low bleeding frequency (less than 2 bleeding episodes over the previous 6 months), could switch to once weekly dosing (75 IU/kg BW). These patients will be allowed to continue on this regimen in pathfinder8.

Patients currently receiving episodic treatment for bleeding episodes (on-demand treatment) will upon entry into pathfinder8 be allowed to switch to either of the prophylaxis regimens as this is seen as beneficial compared to their current episodic treatment.

Based on a weighted mean from published studies representative numbers for mean ABR in severe haemophilia A patients are 24 bleeds/year for patients treated on-demand and 6.8 bleeds/year for patients on prophylactic treatment. The mean observed ABR for patients on on-demand 12 months prior to entry into pathfinder2 was 28.95. At the end of main phase on prophylaxis the mean observed ABR was 6.66. For all patients on on-demand and once weekly prophylaxis regimen the mean ABR at cut-off for submission were 32.52 and 3.89 respectively .

Intensification to twice weekly or even three times weekly prophylaxis can take place at the investigators discretion. Apart from patients dosed once weekly, all patients should preferably stay on a dosing regimen for at least 6 months.

In the NN7088-3885 (pathfinder5) trial the prophylactic dosing regimen is 60 IU/kg BW twice weekly. Due to an expected increased clearance in younger patients. The same dosing will apply for patients < 12 years of age enrolled in pathfinder8 initiated on twice weekly dosing.

For prevention of bleeding during surgery and for treatment of bleeding episodes doses of 20-75 IU/kg BW are to be administered, depending on the surgical procedure and location and severity of the bleed, respectively. The N8-GP dosing regimens are based on phase 1 data from NN7088-3776 (pathfinder1), the first human dose trial, and the treatment guidelines from the World Federation of Hemophilia regarding prevention of bleeding during surgical interventions and treatment of bleeding episodes .

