##### 7.1.1.1 Once weekly prophylaxis regimen (NN7088-3859 (pathfinder2) patients only)

In a sub-set of patients N8-GP may be administered once weekly at a dose of 75 IU/kg BW. Patients are eligible for the once weekly N8-GP dosing regimen if they were treated once weekly or were on the on demand regimen in NN7088-3859 (pathfinder2) upon entry into pathfinder8. The once weekly treatment arm is only available at screening/V1.

If the patient experiences more than 2 bleeds within an 8 week period or experiences a severe bleed requiring hospitalisation, it should be considered to change the patient to a twice weekly regimen. This decision is per investigators discretion in collaboration with the patient.

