### 7.1.1.2 Twice weekly prophylaxis regimen

For twice weekly prophylaxis doses of N8-GP 50 IU/kg BW for patients  $\geq 12$  years of age and 60 IU/kg BW for patients  $< 12$  years of age are to be administered. If a patient reaches the age of 12 years during the trial, he must be switched to 50 IU/kg BW.

At the investigators discretion an intensification of the dosing regimen to three times weekly should be considered if the patient experiences spontaneous bleeding episodes.

If clinically warranted a patient can be switched to three times weekly at any time. Otherwise any treatment regimen should preferably be kept for a minimum of 6 months..

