### 7.1.1.3 Three times weekly prophylaxis regimen

For three times weekly prophylaxis doses of 50 IU/kg BW apply for all patients.

If clinically warranted a patient can be switched to twice weekly at any time. Otherwise any treatment regimen should preferably be kept for a minimum of 6 months.

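### Plasma PEG is measured because of a concern about accumulation, but the SAP specifies only a summary for each of two visits, with no within-patient change and no split by regimen

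*SAP*

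**What the plan says.** SAP 2.6 gives the reason for the measurement as "a general concern from the authorities regarding systemic accumulation of PEG". The planned output is one clause: "concentration of PEG in plasma will be measured at visit 3 plus at the end-of-trial visit, and summarised for each visit". The paragraph names no change from visit 3, no regimen split, no listing or plot, and no rule for patients who switch regimen, who have only one sample, or whose value is below the limit of quantification (LLOQ).

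The protocol sets these nominal doses:
- Once weekly (Protocol 7.1.1.1): "N8-GP may be administered once weekly at a dose of 75 IU/kg BW".
- Twice weekly (Protocol 7.1.1.2): "For twice weekly prophylaxis doses of N8-GP 50 IU/kg BW for patients" aged 12 or over, and 60 IU/kg under 12. The latter is carried over from the paediatric trial, where "the prophylactic dosing regimen is 60 IU/kg BW twice weekly" (Protocol 5.5). A twice-weekly patient who turns 12 changes dose.
- Three times weekly (Protocol 7.1.1.3): "For three times weekly prophylaxis doses of 50 IU/kg BW apply for all patients".

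Switching is part of the design (Protocol 5.1): "The treatment regimen can be changed to twice or three times weekly during the course of the trial". Protocol 7.1.1.3 also allows a move from three times to twice weekly. Protocol 5.2 expects about 170 patients to be assigned and 153 to complete. Protocol 5.2.1 lets a patient complete early, outside the visit windows, once the product is marketed in his country.

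SAP section 3 states: "There are no changes to the statistical analyses described in the protocol". It adds that SAP section 2 has the same text as the protocol's statistical section. Protocol section 10 contains no PEG concentration analysis.

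**The concern.** Accumulation is a rise within a patient over time at a given exposure. Two cross-sectional summaries do not estimate that. They compare the average of whoever was sampled at visit 3, on the dosing of that time, with the average of whoever was sampled at EoT, on the dosing of that later time. If dosing is intensified between the visits, the second summary rises even when no stable patient accumulates. If patients with high levels leave without an EoT sample, the second summary falls even when nobody's level falls, and it can offset a real rise in those who stay.

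At stake is the interpretation of an output added for a safety concern. A reader of the two summaries could take a shift in regimen mix for accumulation, or take a flat pair of means as reassurance.

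The section 3 statement is a separate matter of traceability: an analysis was added and not declared as an addition.

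**Working it through.** The documents attach no figure to the PEG analysis, so there is no planned value to reproduce. The check is arithmetic on a mean per visit.

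**Inputs from the documents**
- Weekly dose (IU/kg): once weekly 75; twice weekly 2 x 50 = 100 (aged 12 or over) or 2 x 60 = 120 (under 12); three times weekly 3 x 50 = 150.
- Ratios: 150/75 = 2.0; 150/100 = 1.5; change at age 12, 100/120 = 0.83.
- Completion: 153/170 = 0.90, so 10% are lost (17 patients).
- Visit 3 is at week 26 and EoT at week 104, a planned gap of 78 weeks.

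**Assumptions not in the documents**
- PEG level is proportional to weekly dose, with no accumulation in a patient whose dose is stable.
- Visit 3 mix is 15/80/5% on once/twice/three times weekly, with every twice-weekly patient at 100 IU/kg/week.

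**1. Switching.** Only net movement after week 26 counts, because earlier switches are already in the visit 3 summary.
- Visit 3 mean (dose units): 0.15 x 75 + 0.80 x 100 + 0.05 x 150 = 98.75.
- If a fraction f of twice-weekly patients moves to three times weekly, the mean rises by 0.80 x f x (150 - 100) = 40f, a relative change of 40f/98.75.

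| f | Rise | Relative change |
|---|---|---|
| 0.10 | 4 | +4.1% |
| 0.20 | 8 | +8.1% |
| 0.30 | 12 | +12.2% |

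- Moving 10% of all patients from once to twice weekly and 10% of all from twice to three times weekly: (0.10 x 25 + 0.10 x 50)/98.75 = 7.5/98.75 = +7.6%.
- Children make the effect smaller: a move from 120 to 150 is +25%, against +50% for 100 to 150.

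**2. Loss of patients.** Let the 10% lost have r times the completers' visit 3 level and give no EoT sample, while every completer stays constant. The relative change in the mean is 1/(0.9 + 0.1r) - 1.
- r = 0.5: 1/0.95 - 1 = +5.3%.
- r = 2.0: 1/1.10 - 1 = -9.1%.
- With a true 10% rise in every completer and r = 2.0: 1.10/1.10 - 1 = 0%.

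This treats all 17 losses as occurring after visit 3. Losses before week 26 do not enter.

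**3. Paired comparison.** Under the same assumptions, the EoT/visit 3 ratio in patients with both samples and an unchanged dose is exactly 1, so both artefacts vanish. At equal n and variance, the standard error of a paired change is sqrt(1 - rho) times the unpaired one: 0.71, 0.55 and 0.32 for an assumed within-patient correlation of 0.5, 0.7 and 0.9.

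**4. What the SAP does elsewhere.** Pre-dose FVIII activity is summarised by visit and by regimen (SAP 2.3.2.1), Hemo-SAT as the change from first to last assessment (SAP 2.3.2.1), and incremental recovery by visit with a listing (SAP 2.5). The PEG paragraph has none of these.

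**The case against.** **Pooling is read from silence.** This is fair. The SAP nowhere says that regimens are combined for PEG, and SAP 2.2 says patients are analysed by treatment received. What stands is that no split is specified. The SAP 2.2 sentence defines no PEG table, and even a split by regimen would leave switchers moving between columns.

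**Other outputs may show the paired values.** SAP 2.6 plans individual profiles of laboratory parameters, which would show both values if PEG counts as one. PEG has its own later paragraph and is absent from the laboratory table in Protocol Appendix 2. Those plots are by age group and give no estimate or interval. SAP 2.4 permits exploratory pharmacokinetic work but commits to none.

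**Most patients would be in both summaries.** This is also fair. Patients who stop product are asked to attend EoT (Protocol section 8), and those moving to commercial product finish through an EoT visit. It would be wrong to say that the two summaries describe different patients. Part of the drop-out effect is unequal follow-up rather than a missing sample.

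**Stronger readings that the documents do not support**
- *The two-fold dose range could hide a rise of 20-30%.* It could not by spread alone. Take half the patients at 75 and half at 150: mean 112.5, SD 37.5, so the coefficient of variation is 1/3. The standard error of the unpaired difference from this source is (1/3) x sqrt(1/170 + 1/153) = 3.7%, and a 20% rise is more than five of these. To cancel 20% by switching, mean dose must fall by 1 - 1/1.2 = 17%. Once weekly is open only at visit 1, and from the assumed mix, moving every three-times-weekly patient to twice weekly lowers the mean by 2.5/98.75 = 2.5%. To cancel 20% by drop-out requires 0.9 + 0.1r = 1.2, so r = 3.
- *The mean moves by 5-15%.* That is 105 to 115 against 100, for a cohort consisting only of twice-weekly patients. It is the ceiling over possible mixes, not the all-patient figure.
- *The authorities' question would go unanswered.* The SAP records only a general concern, and the request itself is not in the documents.

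**It is only a descriptive output.** True: PEG is not a listed endpoint, and no test or decision rule rests on it. That limits the weight of the point but does not remove the gap.

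**Conclusion.** The point holds as a gap in the specified output. For a concern about accumulation, SAP 2.6 commits to two visit summaries, which cannot separate a change in regimen mix or in who was sampled from a change within patients. Under the stated assumptions, the all-patient mean can move by about +4% to +12% from switching, or by +5% to -9% from loss of patients, with no change in any stable patient. A true 10% rise can be fully masked only if the lost 10% had twice the completers' level and gave no EoT sample. All these sizes depend on proportionality to weekly dose and, for switching, on the assumed mix and movement, none of which the documents give.

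The paired analysis has its own limit. All patients were exposed to the product before this trial and no PEG sample before visit 3 is named, so no analysis of these two samples can show accumulation before week 26.

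SAP section 3 is incorrect as written, because the PEG analysis is in SAP 2.6 and not in protocol section 10. This is an improvement worth making to an additional safety output. It does not affect the primary or secondary endpoints.

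**What to change.** Keep the by-visit summary and add the following to SAP 2.6:
- **Paired ratio.** Within-patient EoT/visit 3 ratio with 95% CI, overall and by regimen, in patients with both samples and an unchanged regimen. Define unchanged as the same nominal weekly dose per kg, so that the change at age 12 counts as a change. Report how many patients qualify.
- **Model for all patients with both samples.** Regress log(EoT/visit 3) on log(weekly dose at EoT / weekly dose at visit 3) and on the time between samples, centred at the planned 78 weeks. The intercept is then the log ratio at unchanged dose over 78 weeks. The covariate should be the change in dose, not its level: without accumulation, stable patients at 100 and at 150 IU/kg/week both have a ratio of 1. Define in advance the period over which weekly dose is taken before each sample.
- **Rule for values below LLOQ.** The half-LLOQ rule in SAP 2.3.2.1 is written for FVIII activity. Applied to PEG, it would give a ratio of exactly 1 whenever both values are below LLOQ, so report the number of such pairs and state how they are handled.
- **Stated limit.** Say that the ratio covers week 26 to EoT only.

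In SAP section 3, list the PEG analysis as an addition to the protocol and remove the claim of identical text.

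The cost is SAP wording, one table and one simple model. It uses the two samples the SAP already plans, although the documents do not show how many patients will have both.
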